5.3.2 Intra-Patient Escalation

Intra-patient dose escalation will occur during the first 7 days of Cycle 1 on Dose Level 1 and the first 8 days of Cycle 1 on Dose Levels -1 and 2 as described in [Section 5.1](#). Intra-patient dose escalation occurring outside of this time period is not allowed.

5.4 **Grading of Adverse Events**

Adverse events (toxicities) will be graded according to the NCI Common Terminology Criteria for Adverse Events (CTCAE) version 5.0. All appropriate treatment areas should have access to a copy of the CTCAE version 5.0. A copy of the CTCAE version 5.0 can be downloaded from the CTEP website (http://ctep.cancer.gov/protocolDevelopment/electronic_applications/ctc.htm). Any suspected or confirmed dose-limiting toxicity should be reported immediately (within 24 hours) to the Study Chair.

5.5 **Definition of Dose-Limiting Toxicity (DLT)**

DLT will be defined as any of the following events that are possibly, probably or definitely attributable to protocol therapy. The DLT observation period for the purposes of dose-escalation will be the first cycle of therapy.

Dose limiting hematological and non-hematological toxicities are defined differently.

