¹ PK samples will be collected from all patients during Cycle 1. The PK sampling schedule during Cycle 1 will differ depending on dose level assignment of the patient. See [Section 8.2](#) for details. Blood samples will also be collected 30 minutes, 1 hour, 2 hours, 4 hours, 8 hours, and 24 hours after the end of infusion

on the patient's last day of protocol therapy.

- 2 Women of childbearing potential require a negative pregnancy test prior to starting treatment; sexually active patients must use an acceptable method of birth control. Abstinence is an acceptable method of birth control.
- 3 If patients have Grade 4 neutropenia then CBCs should be checked at least every other day until recovery to Grade 3 or until meeting the criteria for dose limiting toxicity.
- 4 If patients develop Grade 4 neutropenia then CBCs should be checked every 3 to 4 days until recovery to Grade 3.
- 5 Bone marrow aspirate and clot section/biopsy.
- 6 In consenting patients, CD123 site density analysis to be sent to Hematology at baseline (see [Section 8.4](#)).
- 7 In consenting patients only. See [Section 8.5](#) for details.
- 8 In consenting patients, blood samples will be collected on Cycle 1 Days 1, 8, 14, 22, and 29 and on Day 1 of subsequent cycles prior to infusion. See [Section 8.6](#) for details.
- 9 In consenting patients, blood samples will be collected on Cycle 1, Day 1 (pre-infusion) and on Cycle 1, Day 8. Additionally, if patients experience IRR/CRS, blood samples will be collected from consenting patients at the time of IRR/CRS and at the time of IRR/CRS resolution. See [Section 8.7](#) for details.
- 10 ADA samples will be collected from all patients on Cycle 1, Day 1 (pre-infusion), Cycle 3, Day 1 (pre-infusion), Cycle 5, Day 1 (pre-infusion). See [Section 8.3](#) for details.
- 11 In consenting patients, extra bone marrow aspirate will be obtained from the mandatory bone marrow biopsy prior to Cycle 1. See [Section 8.8](#) for details.
- 12 Cytogenetics and FISH will be performed on the collected bone marrow aspirate (it is recommended that cytogenetics/FISH be performed by a COG-approved laboratory).

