8.2.2 Sampling Schedule (See [Appendix VI-A](#), [Appendix VI-B](#), and [Appendix VI-C](#))

The PK sampling schedule will vary according to the dose level assignment of the patient. For all patients being treated on DL1, blood samples will be collected at the following time points*:

- Cycle 1, Day 1: prior to start of infusion
- Cycle 1, Days 3 – 7: 30 minutes prior to syringe change and dose escalation

THIS PROTOCOL IS FOR RESEARCH PURPOSES ONLY, SEE PAGE 1 FOR USAGE POLICY

- Cycle 1, Day 8: 24 hours after Day 7 syringe change and final dose escalation
- Cycle 1, Day 12, Day 15, Day 19, Day 22, Day 27, and Day 29 (prior to infusion ending): any time

For all patients being treated on DL-1, blood samples will be collected at the following time points*:

- Cycle 1, Day 1: prior to start of infusion
- Cycle 1, Day 4, Day 6, and Day 8: 30 minutes prior to syringe change and dose escalation
- Cycle 1, Day 9: 24 hours after Day 8 syringe change and final dose escalation
- Cycle 1, Day 13, Day 17, Day 21, Day 25, and Day 29 (prior to infusion ending): any time

For all patients being treated on DL2, blood samples will be collected at the following time points*:

- Cycle 1, Day 1: prior to start of infusion
- Cycle 1, Days 3 – 8: 30 minutes prior to syringe change and dose escalation
- Cycle 1, Day 9: 24 hours after Day 8 syringe change and final dose escalation
- Cycle 1, Day 13, Day 17, Day 21, Day 25, and Day 29 (prior to infusion ending): any time

*All time points given are for patients that follow the dosing schedule exactly as outlined in [Section 5.1](#). For patients that require dose interruptions during Cycle 1, PK samples should be drawn according to when the patient reaches certain dose levels (see [Appendix VI-A](#), [Appendix VI-B](#), and [Appendix VI-C](#) for details).

Blood samples will also be collected at the following time points on the patient's last day of protocol therapy:

- 30 minutes, 1 hour, 2 hours, 4 hours, 8 hours, and 24 hours after the end of infusion

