8.6.2 Sampling Schedule (See [Appendix X](#))

Blood samples will be collected from consenting patients at the following time points:

- Cycle 1: Day 1 pre-infusion, and Days 8, 15, 22, and 29 (prior to the end of infusion)
- Subsequent cycles, Day 1: Pre-infusion

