APPENDIX IV-B: THERAPY DELIVERY MAP FOR CYCLE 1, DOSE LEVEL -1

Therapy Delivery Map – Cycle 1, Dose Level -1 This Therapy Delivery Map (TDM) relates to Cycle 1. Each cycle lasts 29 days.	Patient COG ID number _____ DOB _____
---	--

Criteria to start each cycle are in [Section 5.2](#). Extensive treatment details are in [Section 5.1](#).

This TDM is on 4 pages. Flotetuzumab therapy ends on Day 29 given continuous infusion administration.

DRUG	ROUTE	DOSAGE		DAYS	IMPORTANT NOTES
IT Cytarabine (ARAC) (all patients)	Intrathecal (IT)	Age-based dosing: Age (yrs) Dose < 1 20 mg 1-1.99 30 mg 2-2.99 50 mg ≥ 3 70 mg		-6 to 0	Patients should receive a single dose of IT cytarabine administered prior to the start of protocol therapy.
Flotetuzumab	Intravenous (IV)	Day Dose 1 30 nanograms/kg/day 2-3 60 nanograms/kg/day 4-5 100 nanograms/kg/day 6-7 200 nanograms/kg/day 8-28 300 nanograms/kg/day		1 – 28	See Section 5.1 for premedications recommendations. See Section 6 for dose modifications for adverse events.

Ht _____ cm

Wt _____ kg

BSA _____ m²

Dose Level _____ nanograms/kg/day

Date Due	Date Given	Day	IT ARAC _____ mg	Flotetuzumab 30 nanograms/kg/ day ng	Flotetuzumab 60 nanograms/kg/ day ng	Flotetuzumab 100 nanograms/kg/day ng	Flotetuzumab 200 nanograms/kg/day ng	Flotetuzumab 300 nanograms/kg/day ng	Studies
Enter calculated dose above and actual dose administered below									
		Pre-	_____ mg	_____ ng	_____ ng	_____ ng	_____ ng	_____ ng	a – d, f – q, u – x
		1	_____ mg	_____ ng	_____ ng	_____ ng	_____ ng	_____ ng	e, r a, b,

THIS PROTOCOL IS FOR RESEARCH PURPOSES ONLY, SEE PAGE 1 FOR USAGE POLICY

									- t	d, f, g
	2			ng						
	3			ng						
	4				ng				e	
	5				ng					
	6					ng			e	
	7					ng				
	8						ng	e, r, s		
	9						ng	e		
	10						ng			
	11						ng			
	12						ng			
	13						ng	e		
	14						ng			
	15						ng	r		
	16						ng			
	17						ng	e		
	18						ng			
	19						ng			
	20						ng			
	21						ng	e		
	22						ng	r		
	23						ng			
	24						ng			
	25						ng	e		
	26						ng			
	27						ng			
	28						ng			
	29									e, i, j, q, r, v, w, y

THIS PROTOCOL IS FOR RESEARCH PURPOSES ONLY, SEE PAGE 1 FOR USAGE POLICY

Required Observations in Cycle 1**All baseline studies must be performed prior to starting protocol therapy unless otherwise indicated below.**

- a. History. Prior to Cycle 1 and every week during Cycle 1.
- b. Physical exam (including VS). Prior to Cycle 1 and every week during Cycle 1.

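### The only routine on-treatment cytokine sample is an untimed Day 8 draw, nominally 24 hours after the final step-up on DL1 but on the day of that step-up on DL-1 and DL2, so its timing is confounded with dose level

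*Combined protocol and SAP*

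**What the plan says.** **Cytokines.** Section 8.1 footnote 9 gives the routine schedule: "blood samples will be collected on Cycle 1, Day 1 (pre-infusion) and on Cycle 1, Day 8". Section 8.7.2 and Appendix XI repeat it. None of them gives a clock time or a relation to the syringe change. The other cytokine samples are event-driven, at onset and at resolution of IRR/CRS.

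**Step-up.** Section 5.3.2 sets intra-patient escalation in the first 7 days of Cycle 1 on DL1 but in "the first 8 days of Cycle 1 on Dose Levels -1 and 2". The delivery maps agree. On DL1 the target dose runs from Day 7. On DL-1 the map reads "8-28 300 nanograms/kg/day", and DL2 likewise reaches its target on Day 8.

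**PK.** Section 8.2.2 follows the step-up. For DL1: "Cycle 1, Day 8: 24 hours after Day 7 syringe change and final dose escalation". For DL-1 and DL2: "Cycle 1, Day 9: 24 hours after Day 8 syringe change and final dose escalation". On those two levels the Day 8 PK sample is taken 30 minutes before the step. The section also re-times PK samples when dosing is interrupted.

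**CD3.** Section 8.6.2 puts the Cycle 1 samples at "Day 1 pre-infusion, and Days 8, 15, 22, and 29" for every level, with Day 1 of later cycles in addition.

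**Delivery maps.** Appendices IV-A, IV-B and IV-C all list PK, CD3 and cytokine draws together on Day 8.

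**The concern.** Aim 1.3.2 asks how cytokine production changes from before to after treatment. For a patient without IRR/CRS, the after value is this one sample. Its position relative to the final escalation is set by the assigned dose level, so a difference between levels could reflect dose, time at target, or both. A description pooled over levels mixes samples taken at target with samples taken just short of it. The period after the last step is also distinct in the plan's own terms: Section 5.1 schedules several prophylactic drugs for 48 hours after it. A nominal DL1 sample lies inside that period and a pre-step DL-1 or DL2 sample lies outside it.

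The PK schedule already allows for the different step-up lengths. The cytokine schedule does not, and the protocol gives no reason for the difference.

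**Working it through.** **Inputs.** Daily infusion rates come from the Section 5.1 tables and Appendix IV, and sampling days from Sections 8.1, 8.2.2 and 8.7.2. The only half-life in the documents is 3.5 hours, in monkeys (Section 2.2.3). No human value is given, so I assume a range of 1.5 to 12 hours. It is used only to illustrate exposure.

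**Step 1: the plan's own figure.** Nominal hours at target on Day 8 = (8 − first day at target) × 24. For DL1 this is (8 − 7) × 24 = 24 hours, which agrees with the DL1 PK schedule.

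**Step 2: all levels.** Rate before the Day 8 change as a share of target = Day 7 rate ÷ target rate.

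| Level | Target (ng/kg/day) | First day at target | Nominal hours at target on Day 8 | Day 7 rate ÷ target |
|---|---|---|---|---|
| DL1 | 500 | 7 | 24 | 500/500 = 100% |
| DL-1 | 300 | 8 | (8 − 8) × 24 = 0 | 200/300 = 67% |
| DL2 | 700 | 8 | (8 − 8) × 24 = 0 | 600/700 = 86% |

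**Step 3: no clock time.** If both the step and the draw may fall at any hour of their calendar days, the sample lies about 0 to 48 hours after the final step on DL1, and about 24 hours before to 24 hours after it on DL-1 and DL2. Only DL1 is certain to be sampled after the step.

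**Step 4: drawn with the Day 8 PK sample.** A site that takes the three listed draws together samples 24 hours after the final step on DL1 and 30 minutes before it on DL-1 and DL2.

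**Step 5: illustration of exposure.** Assume one compartment, linear kinetics and a constant-rate infusion. With the previous step near steady state, concentration as a share of target steady state at h hours after the final step is [previous rate + (target − previous rate) × (1 − 2^(−h/half-life))] ÷ target. With a half-life of 3.5 hours:

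- DL-1: 67% before the step; (200 + 100 × 0.547)/300 = 85% at 4 hours; (200 + 100 × 0.795)/300 = 93% at 8 hours.
- DL2: 86% before the step; (600 + 100 × 0.547)/700 = 94% at 4 hours; (600 + 100 × 0.795)/700 = 97% at 8 hours.
- DL1: about 100% at its nominal 24 hours.

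Summing over all steps for half-lives from 1.5 to 12 hours, the values just before the Day 8 change time are 93–100% on DL1, 65–67% on DL-1 and 81–86% on DL2. The ordering holds over the whole range.

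**The case against.** The case on the other side has substance.

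- **The aim does not ask for a value at target.** By Day 8 every uninterrupted patient has had about a week of drug. No comparison of cytokines between dose levels is planned, the study is optional, and Section 11.5 calls all these analyses descriptive and hypothesis-generating. This limits the stakes. It does not make a pooled description interpretable when timing moves with dose level.
- **Other cytokine samples exist.** In adults at the RP2D, Section 2.3.1 reports IRR/CRS of grade 1 in 25.8%, grade 2 in 58.1% and grade 3 or higher in 12.9%, so many patients may give event-timed samples. Those follow the event, however, and cannot stand in for a common routine time point.
- **Timing can be recovered.** Appendix XI records each draw time and Appendix VI records syringe-change times, so linking them shows whether a sample came before or after the step. This stands, but linkage cannot supply a 24-hour value that was never drawn. The DL2 PK form also labels its Day 7 and Day 8 syringe changes differently from Section 5.1, and its introductory text counts the Day 9 sample from a different day's change than Section 8.2.2 does. Those passages must be reconciled.
- **Re-timing is a trade-off.** It gives up equal time since first exposure. That is true, and the difference is one day.

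A reader might infer that CD3 is equally affected. It is not: Days 15, 22 and 29 are at target on every level if dosing is uninterrupted, so only the Day 8 CD3 value is ambiguous. A reader might also infer that the Day 8 sample on DL-1 and DL2 says nothing about the target dose. Rates of 67% and 86% of target do not support that.

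**Conclusion.** The point holds for cytokines. The one routine on-treatment sample is nominally 24 hours after the final step-up on DL1 and on the day of that step on DL-1 and DL2. It precedes the step there, at 67% and 86% of the target rate, if taken with the Day 8 PK draw. It concerns every consenting patient on DL-1 or DL2, and any on DL1 whose step-up is interrupted. The plan gives no consent rate, so I put no number on them.

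This rests on the Section 5.1 and Appendix IV calendars being followed. The 24 hours on DL1 is taken from the PK schedule, because the cytokine draw itself is untimed.

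The damage is confined to exploratory description and correlation. The documents do not support reading this as a threat to the MTD/RP2D decision, which rests on DLTs. It is worth correcting before DL-1 or DL2 sampling begins, since a mistimed sample cannot be repeated.

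**What to change.** Define the routine on-treatment cytokine sample as 24 hours after the final dose escalation and draw it with the PK sample already due then: Day 8 on DL1, Day 9 on DL-1 and DL2, and later if the step-up is interrupted.

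- Change Section 8.1 footnote 9, Section 8.7.2, the three Cycle 1 delivery maps, the Day 8 CK label in Section 8.7.5, and Appendix XI.
- Add the time of the final syringe change to Appendix XI.
- In Appendix VI, leave the actual day blank on the post-escalation row. It is now pre-printed as Day 8 or Day 9, which does not fit re-timing after an interruption. Reconcile the DL2 form with Sections 5.1 and 8.2.2 in the same edit.
- Keep CD3 on its weekly grid. State the Day 8 draw relative to the syringe change in Section 8.1 footnote 8, Section 8.6.2 and Appendix X, and describe CD3 at target dose from Day 15 onward. Footnote 8 gives Day 14 where Section 8.6.2 and Appendix X give Day 15, and these should be made to agree.

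The cost is schedule, label and form wording. There is no extra sample, blood volume or venipuncture, and no change to dosing. The downside is that time since first exposure at the cytokine sample becomes about 7 days on DL1 (Day 8 − Day 1) and 8 days on DL-1 and DL2 (Day 9 − Day 1). The analysis description should say so.

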8.2 Pharmacology (Required)

8.2.1 Description of Studies and Assay

Pharmacokinetics (PK) will be performed to determine the PK of flotetuzumab in children. Serum samples will be collected and flotetuzumab concentration will be determined by a validated electrochemiluminescent (ECL)-based sandwich assay. Samples will be analyzed by MacroGenics Pharmaceuticals. Bioanalytical measures will be combined with respective individual patient dosing history and demographic information. Pharmacometric analysis will be performed using an appropriate model-based approach. PK parameters will be correlated with toxicity parameters. PK exposures will be compared between patients who achieve CR/CRi and those who do not.

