8.3 Immunogenicity Study (Required)

8.3.1 Description of Studies and Assay

Serum samples will be collected and anti-flotetuzumab antibodies will be detected using a validated bridging immunoassay by a MacroGenics, Inc. bioanalytical lab. Immunogenicity will be compared between patients who achieve CR/CRi and those who do not.

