12.2.2 CR with Partial Recovery of Platelet Count (CRp)

Attainment of an M1 bone marrow (< 5% blasts), no evidence of circulating blasts or extramedullary disease, and recovery of ANC $\geq 1000/\text{mm}^3$ and platelet transfusion independence (defined as no platelet transfusions in 1 week).

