12.2.3 CR with incomplete blood count recovery (CRI)

Attainment of an M1 bone marrow (< 5% blasts), no evidence of circulating blasts or extramedullary disease and with ANC $< 1000/\text{mm}^3$ or platelet count $< 100,000/\text{mm}^3$ without platelet transfusion independence (defined as no platelet transfusions in 1 week).

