12.2.4 Partial Response (PR)

A decrease of at least 50% in the percentage of blasts to 5% to 25% in the bone marrow aspirate. Bone marrow must have adequate cellularity (e.g., > 15%) to determine response. PR status will not be included in calculation of response to the regimen. A repeat bone marrow aspiration after several weeks may be required to distinguish between a PR and increased blasts caused by bone marrow regeneration. A value of < 5% blasts may also be considered a PR if Auer rods are present.

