12.2.6 Stable Disease (SD)

Criteria for CR, CRp, CRI, CRc, PR, or progressive disease (PD) not met.

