12.2.7 Relapse

Morphologic relapse after CR/CRp/CRI is defined as a reappearance of leukemic blasts in the peripheral blood or $\geq 5\%$ blasts in the bone marrow not attributable to any other cause (e.g., bone marrow regeneration after consolidation therapy). In the setting of recent treatment, if there are no circulating blasts and the bone marrow contains 5% to 20% blasts, a repeat bone marrow performed at least a week later is necessary to distinguish relapse from bone marrow regeneration. Should flow cytometric analyses suggest relapse (by the reappearance of a similar immunophenotype to the original leukemia) in the presence of < 5% blasts, or $\geq 5\%$ blasts in a regenerating marrow, a repeat bone marrow(s) performed at least a week later is necessary to confirm relapse by morphologic methods. In such instances the date of recurrence is defined as the first date that more than 5% blasts were observed in the marrow. The

THIS PROTOCOL IS FOR RESEARCH PURPOSES ONLY, SEE PAGE 1 FOR USAGE POLICY

reappearance or development of cytologically proven extramedullary disease also indicates relapse. Molecular and/or genetic relapse is characterized by reappearance of a cytogenetics or molecular abnormality.

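### The PK and ADA comparisons name only CR/CRi as the remission group, so a patient whose best response is CRp falls, read literally, in the non-remission comparator (minor)

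*Combined protocol and SAP*

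**What the plan says.** Two secondary-aim analyses split patients by response. For pharmacokinetics, Section 8.2.1 says "PK exposures will be compared between patients who achieve CR/CRi and those who do not". For immunogenicity, Section 8.3.1 says "Immunogenicity will be compared between patients who achieve CR/CRi and those who do not". Neither sentence mentions CRp.

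Sections 12.2.1 to 12.2.3 define three categories that share an M1 marrow with no circulating blasts and no extramedullary disease. They differ in blood count recovery:

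- **CR:** ANC at least 1000/mm³ and platelets at least 100,000/mm³.
- **CRp:** ANC at least 1000/mm³ and no platelet transfusion for a week.
- **CRi:** ANC below 1000/mm³, or platelets below 100,000/mm³ "without platelet transfusion independence (defined as no platelet transfusions in 1 week").

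Elsewhere CRp is kept apart from CRi but treated as a remission. The stable disease definition in 12.2.6 reads "Criteria for CR, CRp, CRI, CRc, PR, or progressive disease (PD) not met". The relapse definition in 12.2.7 begins "Morphologic relapse after CR/CRp/CRI is defined as a reappearance of leukemic blasts". The one category expressly kept out of the response calculation is PR, in 12.2.4: "PR status will not be included in calculation of response to the regimen".

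Section 11.5 describes the PK, correlative and response analyses as descriptive, exploratory and hypothesis-generating. It gives no responder definition.

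**The concern.** The split in 8.2.1 and 8.3.1 does not match the protocol's own set of remissions. A CRp patient has recovered neutrophils and needs no platelet transfusions, yet belongs to neither named category and so lands in the comparator. A patient with the same neutrophil recovery who still needs platelet transfusions is CRi and lands in the remission group. The better platelet recovery is therefore placed on the worse side, and no reason is given.

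If CRp patients resemble other patients in remission, placing them in the comparator pulls the PK exposure contrast toward no difference. For ADA it blurs the comparator group. In a study expecting only a handful of remissions, deciding where CRp belongs after seeing the data would also be a post hoc choice.

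**Working it through.** The plan attaches no sample size, power or effect size to either comparison, so there is no planned figure to reproduce. The check has three parts.

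**1. Where does each patient go?** Take an M1 marrow with no blasts or extramedullary disease and apply 12.2.1 to 12.2.3 literally. The CRi sentence can be read two ways. In reading A the transfusion phrase qualifies only the platelet clause; in reading B it qualifies both clauses.

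| ANC ≥ 1000 | Platelets ≥ 100,000 | Transfusion independent | Category | Side of the split |
|---|---|---|---|---|
| yes | yes | yes | CR (also meets CRp as written) | CR/CRi |
| yes | yes | no | CR | CR/CRi |
| yes | no | yes | CRp only | comparator |
| yes | no | no | CRi | CR/CRi |
| no | either | no | CRi | CR/CRi |
| no | either | yes | CRi under A; none under B | depends on reading |

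The third row is the point: under either reading it is neither CR nor CRi. Compare it with the fourth row, which differs only in still needing platelet transfusions and counts as a remission. The overlap in the first row does not change the split.

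**2. How much could the PK contrast be diluted?** Let N be the number of patients, r the number with CR/CRi and k the number with CRp as best response. Assume CRp patients have the same mean exposure μR as other remissions, and the rest have mean μN. The comparator has C = N − r patients and mean [k·μR + (C − k)·μN] / C. The observed difference is

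μR − [k·μR + (C − k)·μN] / C = (1 − k/C)(μR − μN),

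so the share of the true difference lost is k/C.

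Inputs: N = 27 is the anticipated maximum in Section 11.1, and the adult CR/CRi rate of 5/27 (18.5%) is from Section 2.3.1. No CRp rate is given, so k from 0 to 3 is an assumption. N = 18 is the Section 11.1 maximum for MTD/RP2D determination, and N = 24 adds the 6 PK expansion patients. For these, r is 24 × 5/27 = 4.4, rounded to 4, and 18 × 5/27 = 3.3, rounded to 3.

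| N | r | C | k = 0 | k = 1 | k = 2 | k = 3 |
|---|---|---|---|---|---|---|
| 27 | 5 | 22 | 0% | 4.5% | 9.1% | 13.6% |
| 24 | 4 | 20 | 0% | 5.0% | 10.0% | 15.0% |
| 18 | 3 | 15 | 0% | 6.7% | 13.3% | 20.0% |

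At N = 27, moving CRp to the remission side changes 5 versus 22 into 6 versus 21, 7 versus 20 or 8 versus 19 for one to three CRp patients.

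**3. Who is in the ADA comparator?** Section 8.3.2 schedules ADA before Cycle 1, Cycle 3 and Cycle 5. Sections 5.1, 5.2 and 10.1 end protocol therapy for progressive disease or for failure to reach at least PR after Cycle 2. Scheduled post-baseline ADA therefore comes mainly from patients with PR or better. Exceptions are patients who start a cycle while awaiting disease evaluation (5.2) and unscheduled samples (8.3.5). The literal post-baseline ADA comparator is mainly PR and CRp, so the C = 22 denominator does not carry over and no dilution figure is offered for ADA.

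**The case against.** The strongest reply is that CR/CRi is shorthand. The adult response list in Section 2.3.1 has no CRp category, so the label may have been carried over with CRp meant to be included. That is possible, but the text does not say so, and an analyst applying Section 12.2 would exclude CRp. It makes this a labelling inconsistency that still needs correcting.

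It is also fair that both comparisons are descriptive, with no test or decision rule attached, and that the data could be regrouped at analysis. Response is the best over up to 4 cycles (12.2), so a CRp patient who later reaches CR is unaffected, and the CRp count may be zero. All of this stands and limits the severity.

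Three stronger readings are tempting but unsupported:

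- **That the PK contrast is diluted by about a fifth.** With about 4.4 CR/CRi expected in 24 patients, one CRp patient would be 1/5.4 = 19% of remissions. But dilution depends on the CRp share of the comparator: 1/19.6, about 5%.
- **That CRp patients are pooled with stable and progressive disease for ADA.** The sampling and discontinuation rules make the scheduled post-baseline comparator mainly PR and CRp. Moving CRp out leaves mostly PR, in an already small group.
- **That CRp is reported as non-response throughout.** Sections 8.2.1 and 8.3.1 define only these two contrasts. Section 11.5 reports response descriptively by the AML criteria, so CRp would still be reported as CRp.

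**Conclusion.** The inconsistency is real: as written, the two comparisons exclude CRp from the remission group, contrary to the remission set in 12.2.7 and with no stated reason. It is minor. For PK, the illustrative dilution of a true mean difference is 0% to about 14% for 0 to 3 CRp patients at N = 27 with 5 CR/CRi, and about 5% for one. The smaller sample sizes shown extend this to 20% at most. These figures rest on an assumed CRp count, the adult CR/CRi rate, and CRp exposure resembling that of other remissions. In so small a sample, attenuation is the expected direction, not a certainty. For ADA the problem is that CRp is grouped mainly with PR. Dose-limiting toxicity, MTD and RP2D determination do not use either contrast.

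**What to change.** In Sections 8.2.1 and 8.3.1, replace CR/CRi with CR/CRp/CRi, so that both comparisons use the remission set of 12.2.7. If leaving CRp out was intended, say so and give the reason in one sentence.

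The cost is a wording change in two sentences. No sampling, treatment, sample size or dose-finding rule changes. Section 11.5 contains no responder definition, so nothing there has to be aligned. The change does not settle two neighbouring gaps: how the CRi sentence applies to ANC below 1000/mm³ with platelet transfusion independence, and the term CRc in 12.2.6, which Section 12.2 does not define. Both could be clarified in the same amendment.
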